sided 95% confidence intervals will be provided for changes within each treatment group. In addition, the differences between each treatment group and placebo will be estimated.

The individual maximum response scores will be defined as the maximum MDS-UPDRS Part III score post dosing from the baseline across all time points post dose (from 15, 30, 45, 60, 90 and 120 minutes for C1, C2, and C3, and 30, 60, 90, 120 minutes for C4) of each subject and will be summarized by treatment groups as well as analysed with an Analysis of Covariance (ANCOVA) model with treatment group as a fixed factor and baseline MDS-UPDRS Part III score as a covariate. The least square (LS) means, standard errors and two-sided 95% confidence intervals will be provided for changes within each treatment group. In addition, the differences between each treatment group and placebo will be estimated.

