All items must have an integer rating (no half points, no missing ratings).

Specific instructions are provided for the testing of each item. These should be followed in all instances. The investigator demonstrates while describing tasks the patient is to perform and rates function immediately thereafter. For Global Spontaneous Movement and Rest Tremor items (3.14 and 3.17), these items have been placed purposefully at the end of the scale because clinical information pertinent to the score will be obtained throughout the entire examination.

At the end of the rating, indicate if dyskinesia (chorea or dystonia) was present at the time of the examination, and if so, whether these movements interfered with the motor examination.

3a Is the patient on medication for treating the symptoms of Parkinson's Disease? No Yes

3b If the patient is receiving medication for treating the symptoms of Parkinson's Disease, mark the patient's clinical state using the following definitions:

ON: On is the typical functional state when patients are receiving medication and have a good response.

OFF: Off is the typical functional state when patients have a poor response in spite of taking medications.

3c Is the patient on Levodopa ? No Yes

3.C1 If yes, minutes since last levodopa dose: _____

	SCORE

3.1 SPEECH
 
Instructions to examiner: Listen to the patient’s free-flowing speech and engage in conversation if necessary. Suggested topics: ask about the patient’s work, hobbies, exercise, or how he got to the doctor’s office. Evaluate volume, modulation (prosody) and clarity, including slurring, palilalia (repetition of syllables) and tachyphemia (rapid speech, running syllables together).
 
0: Normal: No speech problems.
 
1: Slight: Loss of modulation, diction or volume, but still all words easy to understand.
 
2: Mild: Loss of modulation, diction, or volume, with a few words unclear, but the overall sentences easy to follow.
 
3: Moderate: Speech is difficult to understand to the point that some, but not most, sentences are poorly understood.
 
4: Severe: Most speech is difficult to understand or unintelligible.
	

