3.2.2. Secondary Endpoints

1. PK profile of L-dopa for 120 minutes following dosing with INP103 (AUC_{0-2h}, C_{max} and T_{max}).
2. Motor function, evaluated as:
 - Change from baseline to 30 minutes post-dose in Movement Disorder Society Unified Parkinson's Disease Rating Scale (MDS-UPDRS) Part III score (primary motor function endpoint).

- Change from baseline to 15, 30, 45, 60, 90 and 120 minutes post-dose for Cohort 1 (C1), Cohort 2 (C2), Cohort 3 (C3) and change from baseline to 30, 60, 90, 120 minutes for Cohort 4 (C4), in MDS-UPDRS Part III score.
 - Cumulative proportion of responders by post-dose time point (15, 30, 45, 60, 90 and 120 minutes for C1, C2, C3 and change from baseline to 30, 60, 90, 120 minutes for C4), where response is defined as an improvement of 30% in MDS-UPDRS Part III score from baseline.
 - Time to response, where response is defined as an improvement of 30% in MDS-UPDRS Part III score from baseline.
 - Duration of response, where response is defined as an improvement of 30% in MDS-UPDRS Part III score from baseline
 - Area Under the Curve (AUC) of changes in MDS-UPDRS Part III scores from pre-dose to 15, 30, 45, 60, 90 and 120 minutes for C1, C2, C3 and change from baseline to 30, 60, 90, 120 minutes for C4
 - Maximum response in MDS-UPDRS Part III scores from pre-dose to 15, 30, 45, 60, 90 and 120 minutes for C1, C2, C3 and change from baseline to 30, 60, 90, 120 minutes for C4
 - Subjective time to ON, as evaluated by the Investigator and by subject self-assessment
3. The PK/PD_{yn} relationship of single doses of INP103 and motor function

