6.7.3. Change from Baseline

Change from baseline will be calculated as (post-baseline result – baseline result).

6.7.4. Observed Cases (OC) and Last Observation Carried Forward (LOCF), Missing Data and Outliers

Not applicable for this study.

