6.7.6. Other Derivations

Body Mass Index (kg/m^2 , to one decimal place) = Body Weight (kg) / (Height^2 (m)).

For any observed original results above the upper limit or below the lower limit in laboratory assessment, the original results will be presented in data listing and the upper limit value or the lower limit value will be used for summary table. For example, *0.1* will be used if the original result is “<0.1”, while *1000* will be used if the original result is “>=1000”.

Treatment emergent adverse events will be defined as AEs which commence on or after the time of start of first study drug administration. AEs without an onset date or time will be defined as treatment emergent except if an incomplete date (e.g., month and year) clearly indicates that the event started prior to start of first study drug administration or if the AE stop date indicates that the event started and/or stopped prior to start of first study drug administration.

Adverse event time since study drug administration (in minutes) = (Onset Date + Onset Time) – (Study Drug Administration Date + Study Drug Administration Time).

Duration of AE (in minutes) = (Resolution Date + Resolution Time) - (Onset Date + Onset Time).

The response is defined as an improvement of $\geq 30\%$ in MDS-UPDRS Part III score from baseline to post INP103/Placebo dosing time point for each patient.

Time to response = (Time at FIRST response [as defined above] post study drug administration [INP103/Placebo] – Time at the first study drug administration [INP103/Placebo] [Unit = minutes]).

The orthostatic hypotension is defined as a reduction in systolic blood pressure of 20 mmHg or more, and/or a reduction in diastolic blood pressure of 10 mmHg or more, for the standing measurement compared to the supine measurement.

All AUC values will be calculated by using the trapezoidal rule.

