10. EFFICACY ANALYSES

The analyses of PDyn results will be treated as the exploratory analysis of preliminary efficacy in this study and all efficacy analyses will be conducted on the ITT population.

10.1. Change from baseline to 30 minutes post-dose in MDS-UPDRS Part III Score at Visit 3

For each subject, the individual scale from question 3.1 to 3.18 of MDS-UPDRS Part III questionnaire will be added as total score and it will be applied for following analysis of MDS-UPDRS Part III score.

The changes from baseline to 30 minutes post-dose in MDS-UPDRS Part III total score at Visit 3 will be summarized by treatment groups (INP103 35 mg, INP103 70 mg, INP103 140 mg, INP103 70 mg with 7.0 mg carbidopa, or placebo).

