10.5. Duration of response

Duration of response = *sum of all time intervals which observed a response.*

The duration of response will be calculated for each subject and summarized by treatment groups (INP103 35 mg, INP103 70 mg, INP103 140 mg, INP103 70 mg with 7.0 mg carbidopa, or placebo).

For example, if the subject achieves a response at 15, 45 and 90 and 120 minutes (data shown in table below), the duration of response will be calculated as the sum of the duration (95 minutes = 15 minutes + 0 minutes + 0 minutes + 15 minutes + 31 minutes + 34 minutes).

| Schedule Timepoint | Actual Time | Response* | Derivation for Duration of Response* | Duration of Response* |
|--------------------|-------------|-----------|--|-----------------------|
| Pre-dose | 10:00 | NA | NA | |
| 15 mins post dose | 10:15 | Yes | Actual time at "15 mins post-dose" minus the Actual time at "Pre-dose" | 15 |
| 30 mins post dose | 10:30 | No | NA | 0 |
| 45 mins post dose | 10:45 | Yes | Actual time at "45 mins post-dose" minus the Actual time at "30 mins post-dose" | 15 |
| 60 mins post dose | 11:00 | No | NA | 0 |
| 90 mins post dose | 11:31 | Yes | Actual time at "60 mins post-dose" minus the Actual time at "90 mins post-dose" | 31 |
| 120 mins post dose | 12:05 | Yes | Actual time at "90 mins post-dose" minus the Actual time at "120 mins post-dose" | 34 |

* Response is defined as an improvement of at least 30% in MDS-UPDRS Part III score from baseline

10.6. Area Under the Curve (AUC) of changes in MDS-UPDRS Part III scores from pre-dose to post-dose timepoints

AUC of changes in MDS-UPDRS Part III total scores from pre-dose to post-dose will be calculated by trapezoid formula by the following formula:

CONFIDENTIAL AND PROPRIETARY

Area under Curve of (*post-dose total score minus pre-dose total score in MDS-UPDRS Part III score*)

For each subject, AUC of changes in MDS-UPDRS Part III total scores from pre-dose to 15, 30, 45, 60, 90 and 120 minutes for C1, C2 and C3; 30, 60, 90 or 120 minutes for C4 will be calculated as: $AUC_{0-15\text{mins}}$, $AUC_{0-30\text{ mins}}$, $AUC_{0-45\text{ mins}}$, $AUC_{0-60\text{ mins}}$, $AUC_{0-90\text{ mins}}$ and $AUC_{0-120\text{ mins}}$. (omitting $AUC_{0-15\text{ mins}}$ and $AUC_{0-45\text{ mins}}$ for Cohort 4).

These AUC parameters will be summarized by each treatment groups (INP103 35 mg, INP103 70 mg, INP103 140 mg, INP103 70 mg with 7.0 mg carbidopa, or placebo).

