Each AUC parameter ($AUC_{0-15\text{ mins}}$, $AUC_{0-30\text{ mins}}$, $AUC_{0-45\text{ mins}}$, $AUC_{0-60\text{ mins}}$, $AUC_{0-90\text{ mins}}$ and $AUC_{0-120\text{ mins}}$) will be analyzed with an Analysis of Covariance (ANCOVA) model with treatment group as a fixed factor and baseline MDS-UPDRS Part III score as a covariate. The least squares (LS) means, standard errors and two-sided 95% confidence intervals will be provided for changes within each treatment group. In addition, the differences between each treatment group and placebo will be estimated.

10.7. Individual Maximum response in MDS-UPDRS Part III scores from pre-dose to 15, 30, 45, 60, 90 and 120 minutes post-dose.

The individual maximum response scores will be defined as the maximum MDS-UPDRS Part III score post INP103/Placebo dosing from the baseline across all time points post dose (from 15, 30, 45, 60, 90 and 120 minute for C1, C2, C3 and 30, 45, 60, 90, and 120 minutes for C4) for each subject.

The individual maximum response scores will be summarized by each treatment groups INP103 35 mg, INP103 70 mg, INP103 140 mg, INP103 70 mg with 7.0 mg carbidopa, or placebo).

The individual maximum response scores will be analyzed with an ANCOVA model with treatment group as a fixed factor and baseline MDS-UPDRS Part III score as a covariate. The least squares (LS) means, standard errors and two-sided 95% confidence intervals will be provided for changes within each treatment group. In addition, the differences between each active treatment group and placebo and their 95% CIs will be estimated.

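### Maximum response is defined as the highest post-dose Part III score, which is each subject's worst rating or least improvement

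*SAP*

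**What the plan says.** Maximum response is one of the motor-function endpoints in SAP 3.2.2: "Maximum response in MDS-UPDRS Part III scores from pre-dose to 15, 30, 45, 60, 90 and 120 minutes for C1, C2, C3", with 30, 60, 90 and 120 minutes for Cohort 4. SAP 10.7 supplies the derivation: "individual maximum response scores will be defined as the maximum MDS-UPDRS Part III score post INP103/Placebo dosing from the baseline". Protocol 12.5 has the same rule: "maximum MDS-UPDRS Part III score post dosing from the baseline across all time points post dose".

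SAP 10.7 then plans a summary by treatment group (Table 14.2.2.10, marked for the interim analysis in SAP 17.2.2). It also plans an ANCOVA with within-group LS means, confidence intervals and differences from placebo (Table 14.2.2.11, final analysis only).

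Other parts of the plan fix the direction of the scale and the sign of change:

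- **Total score, SAP 10.1:** "the individual scale from question 3.1 to 3.18 of MDS-UPDRS Part III questionnaire will be added as total score".
- **Item anchors, Protocol Appendix 4:** each Part III item runs from 0 (normal) to 4 (severe). Score 4 on item 3.1 reads "Most speech is difficult to understand or unintelligible".
- **Change, SAP 6.7.3:** "Change from baseline will be calculated as" the post-baseline result minus the baseline result. The AUC in SAP 10.6 uses the same sign: "post-dose total score minus pre-dose total score in MDS-UPDRS Part III score".
- **Response, SAP 6.7.6:** "The response is defined as an improvement of" at least 30% in the Part III score.

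**The concern.** A maximum is the right operator for a scale on which higher is better, or for a change computed as baseline minus post-dose. Neither holds here. A programmer who codes SAP 10.7 as worded would report, for each subject, the time at which the drug appeared to do least.

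The within-group means, LS means and confidence intervals would then describe the wrong end of each subject's profile, and an effective dose could appear to produce little or no improvement. SAP 5.1 lists updating the design of future cohorts and planning future studies among the sponsor's uses of the interim results, and the interim output includes Table 14.2.2.10.

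**Working it through.** **Direction.** Items are scored 0 to 4 with 4 the worst, and the total is their sum, so a higher total is worse. Change is post minus baseline, so improvement is negative. SAP 10.7 can be read in two ways:

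- as a raw score, the maximum is the worst rating;
- as a change, the maximum is the least negative value, which is the least improvement.

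Baseline is fixed within a subject, so both readings select the same time point. Neither reading gives the largest improvement.

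**The SAP's own example.** The subject in SAP 10.5 responds at 15, 45, 90 and 120 minutes but not at 30 or 60. Response means a score at or below 70% of baseline and non-response a score above it. The maximum must therefore fall at 30 or 60 minutes, whatever the actual scores. A subject who responds at four of six ratings is given a maximum response below 30%. With an assumed baseline of 40 and assumed scores of 26, 30, 27, 31, 24 and 22, the rule picks 31, a 9-point improvement (9/40 = 22.5%). The largest improvement is 40 - 22 = 18 points (45%).

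**Within-group size.** The documents state no figure for this endpoint, so there is none to reproduce. For independent normal residuals of equal variance, the expected gap between the highest and lowest of n ratings is smallest when the mean profile is flat. That minimum is 2.53 residual SDs for n = 6 and 2.06 for n = 4. For a range of assumed residual SDs:

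| Residual SD (points) | Six ratings, Cohorts 1-3 | Four ratings, Cohort 4 |
|---|---|---|
| 2 | 5.1 | 4.1 |
| 4 | 10.1 | 8.2 |
| 6 | 15.2 | 12.4 |
| 7.8 | 19.8 | 16.1 |

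**Simulation.** The total SD of 11 comes from SAP 4.1.1. It was split into subject/residual SDs of 10.25/4, 9.2/6 or 7.8/7.8 (for example 10.25² + 4² = 121.1, and √121.1 = 11.0). All mean changes at 15, 30, 45, 60, 90 and 120 minutes are assumed:

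- peaked: -4, -8, -11, -12, -10, -6
- early plateau: -8, then -12 throughout
- late plateau: -2, -5, -9, -12, -12, -12
- flat: -6 throughout
- placebo: 0, -1, -1, -2, -1, 0 (0 throughout for the flat case)

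For the peaked profile, the active-group mean over the three splits is -2.0, +0.1 and +2.2 as written, against -14.8, -17.0 and -19.1 for the largest improvement.

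The active-placebo differences are:

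| Profile | As written | Largest improvement | Shrinkage |
|---|---|---|---|
| Flat | -6.0 | -6.0 | none |
| Early plateau | -10.1 to -10.3 | -10.6 to -10.7 | 3-6% |
| Peaked | -6.3 to -7.0 | -8.4 to -8.8 | 17-29% |
| Late plateau | -5.0 to -6.3 | -9.0 to -9.6 | 30-48% |

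**Unequal numbers of ratings, direction corrected.** An extreme over six ratings is larger than one over four. Six placebo subjects have six ratings each, and two or three have four. Comparing Cohort 4 with this pooled group moves the difference toward zero by 0.5 to 1.4 points across the same profiles.

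**Two smaller wording points.** SAP 10.7 lists 45 minutes for Cohort 4, but Protocol 7.4.3 and SAP 10.2 and 10.3 schedule no such rating; results are unaffected. In SAP 10.5 the first response interval starts at the pre-dose time. The example equates this with dosing, but it could be read as the time of the pre-dose rating. If that rating were 5, 15 or 30 minutes before dosing (assumed), the example's 95 minutes would become 100, 110 or 125. The 90- and 120-minute rows also word the subtraction backwards, although the printed 31 and 34 are right.

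**The case against.** The strongest reply is that the intent is plain. The endpoint is called maximum response, response means improvement elsewhere in the SAP, and a sensible programmer would probably code the largest reduction. The reference to baseline and to LS means for changes also suggests that a change was meant, not a raw score. Both points are fair, and least improvement is the better description of what the literal text yields. They do not rescue the rule, because under SAP 6.7.3 the maximum change is still the wrong end. Protocol 12.5 repeats the wording. The table shells mentioned in SAP 6.4 are not in the text available, so they could carry a different rule.

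The consequences are limited. SAP 10 treats the motor analyses as exploratory, there are no formal hypotheses, both tables are priority 2, and SAP 5.1 calls the interim informational with no stopping rule. Every Part III score is listed, so the variable can be re-derived.

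The within-group minimum also depends on independent residuals, and ratings 15 to 30 minutes apart may well be correlated. With a flat profile and a residual correlation of 0.5, 0.7 or 0.8 per 15 minutes, 2.53 falls to about 2.25, 1.94 or 1.68, and 2.06 to about 1.90, 1.65 or 1.43. This lowers the size but leaves the direction unchanged.

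One detail bears on the remedy. SAP 6.4 and 8.5.3 admit unscheduled measurements to summaries that are not time-specific, and give maximum post-dose values as an example. SAP 8 keeps unscheduled-visit data out of summary tables. The revised definition should settle this.

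**Conclusion.** The concern holds. As written, the rule returns the opposite extreme from the one the endpoint names, and no passage in the available text reverses the sign. That conclusion rests on the documents alone.

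The size rests on assumptions. The within-group error is likely to be several points or more for plausible residual SDs. The effect on the active-placebo difference ranges from nil for a flat effect to about half for a late plateau. This should be fixed, but it does not threaten the trial's main conclusions. The two smaller wording points would not merit a comment on their own.

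**What to change.** In SAP 10.7, define maximum response as the most negative change from baseline, that is, the minimum post-dose Part III total minus baseline, over the scheduled times for the cohort. State the sign, say that unscheduled ratings are not used, and delete 45 minutes for Cohort 4. If the interim version of Table 14.2.2.10 has already been produced, record which direction it used.

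At the same time, clarify in SAP 10.5 that the first interval starts at INP103 or placebo dosing, as time to response does in SAP 10.4, and correct the order of subtraction in the last two rows. A sensitivity analysis of Cohort 4 against placebo restricted to 30, 60, 90 and 120 minutes is optional.

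The cost is SAP wording and one derived variable, with no new data. Protocol 12 says the SAP prevails where the two differ, so no protocol amendment is needed.

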10.2. Change from baseline to post-dose timepoints in MDS-UPDRS Part III score

The changes from baseline in MDS-UPDRS Part III score will be summarized by time point (15, 30, 45, 60, 90 or 120 minutes for C1, C2 and C3; 30, 60, 90 or 120 minutes for C4) and treatment groups (INP103 35 mg, INP103 70 mg, INP103 140 mg, INP103 70mg with 7.0 mg carbidopa or placebo). In addition, the changes from baseline in MDS-UPDRS Part III score will be estimated using a Mixed Model for Repeated Measures (MMRM) with treatment group, time, and the interaction between treatment group and time point as fixed factors, and the baseline total score will be included as a covariate. The focus will be on the estimation of changes within each treatment group. An unstructured covariance structure will be used for the MMRM. In case the model does not converge with the unstructured covariance structure, the heterogeneous compound symmetry (CSH) or heterogeneous Toeplitz structure (TOEPH) will be used instead. The denominator degrees of freedom will be approximated using the Kenward-Roger method. The least squares (LS) means, standard errors and two-sided 95% confidence intervals will be provided for changes across time points within each treatment group.

In addition, the differences between each treatment group and placebo will be estimated across time points based on the same MMRM model, and LS mean, standard errors and 95% CI of differences will be presented.

Change from baseline in MDS-UPDRS III score will be plotted by each treatment group for each subject (y axis) against time from dosing (x-axis).

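### Maximum response: the within-group 95% CI in SAP 10.7 has no zero reference, because the mean of each subject's most extreme rating is non-zero when nothing changes

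*SAP*

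**What the plan says.** SAP 10.7 defines the endpoint thus: "The individual maximum response scores will be defined as the maximum MDS-UPDRS Part III score post INP103/Placebo dosing from the baseline across all time points". The ratings listed are "from 15, 30, 45, 60, 90 and 120 minute for C1, C2, C3 and 30, 45, 60, 90, and 120 minutes for C4". SAP 10.2 gives a different Cohort 4 list: "15, 30, 45, 60, 90 or 120 minutes for C1, C2 and C3; 30, 60, 90 or 120 minutes for C4". The endpoint lists in both documents and the protocol's schedule table also give Cohort 4 four times.

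The model is stated in these words: "The individual maximum response scores will be analyzed with an ANCOVA model with treatment group as a fixed factor and baseline MDS-UPDRS Part III score". Baseline enters it as the covariate. Two outputs follow. Within groups: "The least squares (LS) means, standard errors and two-sided 95% confidence intervals will be provided for changes within each treatment group". Between groups: "the differences between each active treatment group and placebo and their 95% CIs will be estimated". Protocol 12.5 has the same within-group output ("confidence intervals will be provided for changes within each treatment group") and also estimates differences from placebo.

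Placebo subjects from all cohorts form one group (SAP 7.1). The results go to Table 14.2.2.10 (summary, also an interim output) and Table 14.2.2.11 (ANCOVA, final analysis only). Neither document says that the no-change value of this quantity is other than zero.

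**The concern.** A reader compares a within-group change with zero. For a change at a fixed time that is correct: if nothing happens, its mean is zero. For the extreme of several noisy ratings it is not. Picking the best of six moves every subject's value towards improvement, and picking the worst moves it towards worsening by the same amount. Every group then shows a shift of several points, produced by the choice of rating alone.

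The plan makes this reading likely. Protocol 12.1 justifies the sample size by a 13-point improvement from baseline within a dose level and says that the study is not powered for between-group comparisons of these endpoints. SAP 10.2 puts the focus of the repeated-measures model on within-group change. A reader could set a no-change maximum response of several points beside the 13-point target and take it as evidence of effect.

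**Working it through.** **Inputs from the documents.** SD of change 11, two-sided 5% level (protocol 12.1, SAP 4.1.1). Six active subjects per group and 2 × 4 = 8 pooled placebo. Six ratings in Cohorts 1–3 and four in Cohort 4. ANCOVA with five groups and a baseline covariate, so 32 − 6 = 26 residual df.

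**Assumed, because not given.** Correlation rho between a subject's changes: 0.5 to 0.9. Independent, equal-variance rating errors around a stable score give 0.5, because all changes share one baseline. Between-subject SD of the baseline score: 12.

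**The plan's own figure.** The documents give no figure for maximum response. The stated 80% power for 13 points, SD 11, n = 8 reproduces as a one-sample t-test (81.7%). A two-sample 8 v 8 t-test gives 59.5%. So the design figure is a within-group change from baseline.

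**No-change mean.** For k equally correlated normal changes with mean zero, the expected extreme is c_k × SD × √(1 − rho), with c_4 = 1.030, c_5 = 1.163 and c_6 = 1.267.

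- Cohort 1–3 dose, rho 0.5: 1.267 × 11 × 0.707 = 9.9 points; rho 0.7: 7.6; rho 0.9: 4.4.
- Cohort 4 (four ratings): 8.0, 6.2 and 3.6.
- Pooled placebo (six subjects with six ratings, two with four), rho 0.5: (6 × 9.86 + 2 × 8.01)/8 = 9.4.

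Against the 13-point target, the Cohort 1–3 values are 9.9/13 = 76% down to 4.4/13 = 34%.

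**Interval against zero, by hand.** The variance of the extreme is SD² × [rho + (1 − rho) × 0.645²] for k = 6, where 0.645 is the SD of the largest of six standard normals. At rho 0.5 this is 121 × 0.708 = 85.7, so the SD is 9.26 and the SE for n = 6 is 3.78. With t(26) = 2.056 the half-width is about 7.8, less than the no-change mean of 9.9, so a typical interval excludes zero. At rho 0.9 the half-width is about 9.0 against 4.4.

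**Simulation of the SAP's ANCOVA, true change zero at every time.** Each range covers two error models. At the low end, the part shared by a subject's changes is unrelated to the observed baseline. At the high end, it is all baseline rating error, which the covariate partly removes.

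| rho | Cohort 1–3 dose: CI excludes zero | Cohort 4 | Placebo | Three or more of five groups |
|---|---|---|---|---|
| 0.5 | 69–78% | 51–60% | 77–85% | 79–89% |
| 0.7 | 42–56% | 30–41% | 50–64% | 35–58% |
| 0.9 | 16–25% | 12–19% | 18–29% | 4–15% |

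The same ANCOVA on the change at 30 minutes alone excludes zero in about 5% of trials per group, so choosing the extreme is the cause. The rates hardly depend on the SD of 11, since shift and interval width scale together. The shift in points is proportional to it. At rho 0.5, in the high-end model, a baseline SD of 6 to 20 moves the placebo rate between 94% and 80%.

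**Difference from placebo.** For a Cohort 1–3 dose the CI excludes zero in 5% of no-change trials. The mean offset is ¼ × (1.267 − 1.030) × 11 × √(1 − rho), which is 0.5 points at rho 0.5 and 0.2 at 0.9.

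For Cohort 4 the offset is larger, because six of the eight placebo subjects have six ratings: ¾ × (1.267 − 1.030) × 11 × √(1 − rho) = 1.4 points at rho 0.5 and 0.6 at 0.9. If the best rating is meant, this counts against Cohort 4. Its rejection rate is 5% to 7%. When every subject's maximum is taken over 30, 60, 90 and 120 minutes, the simulated offset is zero within simulation error and rejection returns to about 5%.

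**The case against.** The strongest reply is that no test against zero is planned. SAP 3.3 and 3.4 state no formal hypotheses, SAP 10 calls these analyses exploratory, and the main motor endpoint is the fixed 30-minute change, which involves no selection. The interval correctly covers the mean maximum response. The placebo mean would stand beside each dose, and the difference from placebo with its CI is already planned.

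Most of this stands. A reader might infer that the plan contains an invalid test or an invalid interval; it contains neither. But a 95% CI labelled as a within-group change invites comparison with zero, and the documents nowhere warn against it.

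Three other strong readings also fail.

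- That most groups will exclude zero: across five groups this is the likelier outcome only up to a correlation of roughly 0.65, and the documents do not give the correlation.
- That a false improvement will be reported: read literally, the maximum score is the worst rating, and the shift is then towards worsening. If the raw score is meant, zero is no reference at all.
- That the difference from placebo removes the problem for every group: it does nearly so for Cohorts 1–3, but not for Cohort 4 on its four-rating schedule.

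**Conclusion.** The point holds as a flaw of reporting and interpretation in one secondary, exploratory endpoint. The within-group mean of maximum response has a no-change value of about 4 to 10 points for a Cohort 1–3 dose at SD 11 and correlation 0.9 to 0.5. Its 95% CI excludes zero well above the nominal 5% at every correlation in that range: roughly 80% (dose) and 85% (placebo) at 0.5 in the baseline-error model, and at least 16% and 18% at 0.9. These sizes rest on the assumed correlation and error model; that the mean is non-zero needs only a correlation below 1. The difference from placebo is the sound comparison, once Cohort 4 and placebo are rated over the same times. The change is worth making before the tables are produced, but it does not touch the 30-minute endpoint or the safety objective.

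**What to change.** Amend SAP 10.7. It supersedes the protocol where the two differ (protocol 12), so protocol 12.5 need not be amended for this.

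1. Show within-group maximum response as mean, SD, median and range only. Make the already planned difference from placebo with its 95% CI the only inferential output of Table 14.2.2.11.
2. Footnote Tables 14.2.2.10 and 14.2.2.11: the maximum over repeated ratings is non-zero on average without any treatment effect and is not to be read against zero.
3. For Cohort 4 versus pooled placebo, take the maximum over 30, 60, 90 and 120 minutes in all subjects. Reconcile the five Cohort 4 times in SAP 10.7 with the four listed elsewhere.
4. State in the definition whether the maximum is the largest improvement or the highest score.

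Cost: SAP wording, one table shell and two footnotes, with no new data. One set of within-group intervals is dropped, and the Cohort 4 comparison leaves the 15 and 45 minute ratings unused.
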